- (i) removal of a withdrawal criterion: "Local therapy after 2nd cycle of study treatment", in line with Steering Committee recommendations to perform analysis on local treatment received after VI/VIT, in order to explain the much larger effect of VIT compared to VI on overall survival than progression-free survival ; and clarification of the Last Visit of the Last Subject (LVLS), defined as the last VI/VIT administration followed by 6 months to have relevant data in terms of response after 2 cycles

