5. INTRODUCTION AND STUDY RATIONALE

5.1. Study disease

Rhabdomyosarcoma (RMS) is a soft tissue sarcoma derived from muscle precursor cells. It is the commonest form of soft tissue sarcoma in children < 15yrs, accounting for around 4% of paediatric malignancies and with a peak incidence in young children < 5yrs. However, RMS can occur at all ages and overall 41% of cases occur in the adult population [Sultan 2009]. The pattern of disease changes with age, with alveolar and metastatic tumours commoner in older children/young people and pleomorphic RMS and not otherwise specified histologies commoner in adults. Adults are more likely to present with disease at unfavourable sites. The likely outcome in RMS depends on a number of risk factors at presentation including age, site, tumour size, histo-logy and presence of nodal or metastatic disease and initial treatment is now tailored according to risk.

Around 85% of children with RMS have localised disease at presentation. Within the SIOP experience the 3 yr event free survival of patients achieving complete local control is 64% and 36% of patients who relapse can be salvaged [Chisholm 2011]. Among patients experiencing relapse, the most frequent site of relapse is locoregional (76%) with only 15% of patients having an isolated metastatic recurrence [Chisholm 2010]. Survival after relapse is affected by several factors, the most important being the type of recurrence, previous radiotherapy, time of relapse and the initial tumour size [Chisholm 2010]. Survival after an isolated local relapse is around 50% at 3 years whereas it is only 13-14% at 3 years after a metastatic relapse [Dantonello 2008, Mattke 2009, Mazzolini 2005, Pappo 1999, Pappo 2001, Pappo 2007, Chisholm et al 2010]. This finding means that we urgently need new chemotherapy agents and/or targeted agents for systemic treatment of RMS. Another key factor is the ability to deliver good local therapy to locally relapsing tumours; where patients have previously received radiotherapy, local therapy may be limited to aggressive surgery. Surgical clearance may be aided by effective new systemic therapies justifying the use of volumetric response of the target lesions to the chemotherapy as the main evaluation criteria in the current study.

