9. TREATMENT ADMINISTRATION

9.1. Starting doses and schedules

ARM A		
D1 and D8 Vincristine	1.5 mg/m ² /d – IV bolus (0.05 mg/kg for patient ≤ 10 kg)	3 weekly
D1 to D5 Irinotecan	50 mg/m ² /d – IV over 1 hour	3 weekly
ARM B		
D1 to D5 Temozolomide	125 mg/m ² /d - PO	3 weekly
D1 and D8 Vincristine	1.5 mg/m ² /d – IV bolus (0.05 mg/kg for patient ≤ 10 kg)	3 weekly
D1 to D5 Irinotecan	50 mg/m ² /d – IV over 1 hour	3 weekly

Vincristine: The dose of vincristine will be 1.5 mg/m² or 0.05 mg/kg for patient ≤ 10 kg (maximum 2.0 mg) and will be administered by direct intravenous infusion on day 1 and day 8 of each course, before irinotecan. Administration must comply with guidance on administration of vinca alkaloids as per NPSA/2008/RRR004.

Irinotecan: The dose of irinotecan will be 50 mg/m²/day. Irinotecan will be given intravenously infusion over 1 hour on days 1-5, one hour following the administration of TMZ. In absence of contraindications (known allergies), **systematic treatment with oral cefixime 8 mg/kg once a day (maximum daily dose 400 mg) is recommended and will be started 2 days before chemotherapy until day 7** (see Appendix 11 for cefixime management in The Netherlands).

Temozolomide: will be given according to the randomization: The starting dose of TMZ will be 125 mg/m²/day. The dose of TMZ will be escalated to 150 mg/m²/day at cycle 2 for patients who do not experience ≥ grade 3 toxicity of any kind. The dose of TMZ should be rounded to the nearest 5 mg. TMZ will be given orally, on an empty stomach, prior to vincristine and irinotecan, on days 1-5 repeated every 3-weeks. If the patient vomits within 20 minutes after TMZ, the dose will be re-administered. The capsules must be swallowed whole with a glass of water. For young children and patients who have difficulty swallowing capsules, the full daily dose of TMZ capsules should be placed

in 10-30 ml fruit juice or compote and administered after the capsules have been allowed to soften for 15-20 minutes or according to normal local practice for patients in the United Kingdom (see Appendix 12).

Treatment will continue until disease progression, unacceptable toxicity or the patient's desire to discontinue therapy. Local treatment is allowed after 2 cycles.

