10.2.3 End of study treatment / Withdrawal procedures

The duration of study participation is a maximum of 12 cycles. However, the continuation of treatment can be individually discussed with the investigator for patients who do not experience progression of disease after 12 cycles.

The following evaluation is performed 3 weeks after the last cycle of chemotherapy or at the end of study (see 7.2.).

Type of Assessment	Delay for End of Study treatment or Withdrawal

CLINICAL EXAM
 
 • Full physical examination • height, weight, body surface • Vital signs : blood pressure after 5 min at rest, heart rate, temperature • Performance status (Lansky Play Score or Karnofsky Score – appendix 3-4) • Assessment of adverse events according to the NCI-CTC AE v.4.0 (appendix 5) • Recording of concomitant medications 	
To be performed 3 weeks after the last cycle of chemotherapy or at the end of study

LABORATORY TESTS
 
 • Complete blood count : white count (WBC), hemoglobin (HGB), hematocrit (HCT), differential count and platelet count • Serum chemistries : glucose, urea, creatinine, total protein, albumin, Ca+, phosphorus and electrolytes (sodium, potassium, chloride and bicarbonate), AST, ALT, total bilirubin, alkaline phosphatase, LDH, GGT 	
To be performed 3 weeks after the last cycle of chemotherapy or at the end of study

RADIOLOGICAL AND OTHER INVESTIGATIONS
 
 • Tumor assessments (CT scan and/or MRI) including measurement of target lesion and assessment of response to treatment should be loaded the CDs onto the PACS system for later review. • Bone scan or FDG-PET Scan* • BM aspirates and trephine biopsies* 	
Mandatory
 
To be performed 3 weeks after the last cycle of chemotherapy or at the end of study, except documented previous disease progression

**only repeated if clinically indicated or if initially involved or to confirm tumor response*

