A clinical assessment should be done at each visit in order to detect tumour progression at any point during treatment. This should be supplemented by radiological examination as appropriate.

RELATIONSHIP BETWEEN CHANGE IN SINGLE DIAMETER (RECIST), PRODUCT OF TWO DIAMETERS (WHO), AND THREE PERPENDICULAR DIAMETERS ("VOLUME")

	Diameter, 2R	Product,(2R) ²	Volume, 4/3πR ³
Response	Decrease	Decrease	Decrease
	13%	24%	33%
	30%	50%	65%
	50%	75%	87%
Disease Progression	Increase	Increase	Increase
	12%	25%	40%
	20%	44%	73%
	25%	56%	95%
	30%	69%	120%

Response evaluation criteria (Volumetric)

Complete Response (CR)	Complete disappearance of all visible disease
Partial Response (PR>2/3)	≥ 65% reduction of tumour volume (volume response between 65-99%)
Minor Partial Response (PR<2/3)	Volume response between 34-64%
Stable Disease (SD)	No criteria for PR or PD
Progressive Disease (PD)	Any increase of more than 73% of any one target lesion/tumour volume or appearance of new lesions.

All responses must last at least 4 to 5 weeks without evidence of tumour progression or relapse.

Metastatic Disease Measurement

The RECIST 1.1 (*European Journal of Cancer 2009; 45: 228–47*) criteria will be used for assessment of the size of measurable metastases, including nodal metastases.

RECIST Methodology

Planes and techniques:

- CT: The same method of assessment and the same technique should be used to characterize each identified and reported lesion at baseline and during follow-up. Lesions should be measured on the same window setting on each examination.
- MRI: Lesions must be measured in the same anatomic plane by use of the same imaging sequences on subsequent examinations.

Measurements:

DIAGNOSIS

- **Measurable lesion:** A lesion that can be accurately measured in at least 1 dimension with the longest diameter at least twice the thickness of the CT or MR slice with a minimum of 10 mm (for lymph nodes ≥15 mm shortest axis). This is defined as a "**target lesion**". The investigator will identify up to 5 target lesions total and up to 2 per organ to be followed for response. In general, the largest lesions representative of involved organs are selected to follow as target lesions. However, in some cases, the largest lesions may not be easily measured and are not suitable for follow-up because of their configuration. In these cases, identification of the largest most reproducible lesions is advised. Serial measurements of

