11.1.3. Objective tumour response and progression

Primary efficacy endpoint

The primary efficacy endpoint is defined as the proportion of patients who had a documented complete or partial tumour response occurring after the first 2 cycles of treatment which must be confirmed by a follow-up objective tumour assessment obtained within 4-5 weeks after the initial documentation.

Secondary endpoints

Secondary efficacy endpoints are defined as follows:

- The best overall response is the best response recorded from the start of the treatment until disease progression/recurrence (taking as reference for PD the smallest measurements recorded since the treatment started) over the whole treatment duration. It must be confirmed by a follow-up objective tumour assessment obtained within 4-5 weeks after the initial documentation.
- Duration of tumour response: the time from first documentation of objective tumour response to the first objective or clinical documentation of progression
- Time to treatment failure: the time from the date of first treatment administration to the first documentation of tumour progression, discontinuation of study treatment before one year, or death, whichever occurs first
- Progression-free survival (PFS): the time from the date of first treatment administration to the date of first objective or clinical documentation of tumour progression or death due to any cause
- Overall survival (OS): the time from the date of first treatment administration to date of death

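### Best overall response has no cut at local treatment, so surgery or radiotherapy after cycle 2 can be counted as response to VI or VIT

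*Protocol*

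**What the plan says.** All references are to the protocol.

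- **Window for best overall response (section 11.1.3).** "The best overall response is the best response recorded from the start of the treatment until disease progression/recurrence", assessed "over the whole treatment duration". Confirmation is required: "It must be confirmed by a follow-up objective tumour assessment obtained within 4-5 weeks after the initial documentation".
- **Local treatment (section 9.1).** "Local treatment is allowed after 2 cycles". In the same section, VI or VIT continues until progression, unacceptable toxicity or the patient's wish to stop.
- **Withdrawal (section 7.8 and the version history).** The current list of reasons for leaving study treatment does not include local therapy. The version history records that version 5.1 of June 2019 removed that criterion.
- **Length of treatment (section 10.2.3).** "The duration of study participation is a maximum of 12 cycles", with continuation beyond that open to discussion.
- **Complete response (section 11.1.1, volumetric criteria).** "Complete disappearance of all visible disease". The criterion for metastatic target lesions and the overall response table in section 11.1.2 likewise do not ask why a lesion disappeared.
- **Expected role of surgery (section 5.1).** "Surgical clearance may be aided by effective new systemic therapies".
- **Comparison (section 12.2, text added after amendment 5.0).** VIT is compared with VI on all efficacy endpoints.

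**The concern.** The response window closes only at progression or recurrence. Local treatment may start early in that window and does not close it. Take a patient with stable disease at the cycle-2 scan who then has all assessed disease removed or irradiated and stays on chemotherapy. Later scans show no visible disease, and under the written definition that is a complete response credited to the randomised regimen.

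Best overall response then reflects partly the drugs and partly the access to, and choice of, local therapy. Treatment is not blinded, so use of local therapy could differ between arms, and such a difference would appear as a difference in drug activity. The version history shows that local treatment is already under study as an explanation for a larger VIT effect on overall survival than on progression-free survival. The response definition does not separate out the same factor.

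The primary endpoint has a smaller exposure. The cycle-2 scan precedes permitted local treatment, but the confirming scan 4-5 weeks later does not.

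**Working it through.** No figure in the protocol is in dispute. The check is a reading of the rules together, followed by a scale calculation.

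**Step 1: does local treatment end the window?** Under section 9.1 it may be given while VI or VIT continues. Section 7.8 does not make it a reason to stop. Section 11.1.3 ends the window at progression or recurrence and ties it to treatment duration. So it does not. With up to 12 cycles of 3 weeks, the part of the window open to local treatment is up to 12 − 2 = 10 cycles, or 10 × 3 = 30 weeks.

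**Step 2: does another rule discount later scans?** Three places come close.
- Section 7.4 keeps the main target lesion free of concurrent radiotherapy, but only palliative radiotherapy, and as an entry condition.
- Section 13.9 asks sites to record another treatment only as a reason for stopping study treatment. It attaches no response rule to it.
- Section 11.1.1 describes the volumetric method as serving neoadjuvant assessment. That states a purpose and sets no cut-off.

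**Step 3: what must happen for a conversion?** Under section 11.1.2 the primary tumour and target lesions must all reach the required response, with no new lesions and no progression. Sections 7.8 and 9.1 end study treatment if a cycle is delayed by more than 2 weeks. The patient must therefore have all those sites dealt with, stay on VI or VIT without such a delay, and have a confirming scan. Treating one site while other measurable disease persists does not produce a responder.

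**Step 4: primary endpoint.** The first reading is after cycle 2, before local treatment is allowed. If that order is kept, local treatment cannot create the initial response. It can matter only for a cycle-2 complete or partial responder who has local treatment before the confirming scan and would otherwise have failed confirmation.

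**Step 5: scale per patient.** Section 12.1 gives 54 relapse patients per arm. All 120 patients give 120/2 = 60 per arm.
- 1/54 = 1.9 percentage points
- 1/60 = 1.7 percentage points

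**Step 6: illustration of a difference between arms.** Let p be the response rate due to chemotherapy, equal in both arms, and q the share of non-responders recorded as responders only through local treatment.

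Apparent rate = p + (1 − p)q, so the spurious difference = (1 − p)(q₁ − q₂).

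The protocol gives no q, so every q here is assumed. For p, the design rates 0.35 and 0.55 in section 12.1 are borrowed, with 0.45 as a middle value. They were set for the primary endpoint, so their use here is also an assumption.

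| p | 1 − p | q₁ − q₂ = 0.10 | q₁ − q₂ = 0.20 |
|---|---|---|---|
| 0.55 | 0.45 | 4.5 points | 9.0 points |
| 0.45 | 0.55 | 5.5 points | 11.0 points |
| 0.35 | 0.65 | 6.5 points | 13.0 points |

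If q is the same in both arms, the spurious difference is zero, although both rates are still raised.

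**The case against.** **The endpoint is secondary and drives no decision.** Section 6.2 sets out to describe best overall response. The activity rule in section 12.1 (at least 22 of 47) concerns the primary endpoint. This stands and limits the weight of the point. A reader might infer that the go/no-go decision is contaminated. The protocol does not support that, because the cycle-2 reading comes before permitted local treatment.

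**A cut at new treatment is often left to the analysis plan.** One not shown here could contain it. But section 11.1.3 itself fixes where the window starts and ends, so a cut made elsewhere would depart from the protocol's own definition.

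**The scenario is narrow.** All relevant sites must respond, treatment must continue without a long delay, and confirmation is needed. This stands and argues for modest numbers, not for none.

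**Timing.** The withdrawal criterion was removed only in June 2019. The 40 extra patients were added by the December 2015 amendment and expected to take about one year. On that plan few patients would still have been on treatment at the removal. This is a fair inference, but actual accrual dates are not given, so it cannot be settled from the protocol.

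**Local treatment is already to be analysed.** True, but the stated purpose is to explain overall survival against progression-free survival, not to define response.

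**A plain cut brings its own bias.** A true responder at cycle 4 who is resected before the confirming scan would count as unconfirmed, which penalises the arm that reaches surgery sooner. This stands, and the fix has to allow for it.

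**Conclusion.** The point holds for best overall response. As written, the definition lets disease cleared by surgery or radiotherapy count as response to VI or VIT, and no other section prevents it. This should be corrected, but it does not threaten the primary conclusion.

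For the primary endpoint the exposure is confined to the confirmation scan. No size can be given for it.

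The size for best overall response is also unknown. What follows from the protocol is 1.7 to 1.9 points per converted patient in an arm of 60 or 54. A reader might take the 5.5 and 11 points, or the wider spans of 4.5-6.5 and 9-13, as estimates of bias. They are illustrations that rest on assumed conversion rates and borrowed response rates. The protocol does not show that local treatment was used more in one arm.

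**What to change.** In section 11.1.3:

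1. Base best overall response on assessments made before progression or recurrence and before the first local treatment (surgery or radiotherapy) to an assessed lesion.
2. Put responses first documented before local treatment but confirmed only after it in a separate category.
3. Report the best overall response rate in each arm without that category, with it, and with no cut at local treatment.
4. For the primary endpoint, flag cycle-2 responders whose confirming scan follows local treatment. Show the response rate with these patients counted as confirmed and as unconfirmed.
5. Optionally, add a sensitivity analysis of duration of response with a cut at local treatment. Counting through later therapy is a legitimate main choice.

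**Cost.** The changes are to definitions and analysis. Best overall response becomes slightly lower, and the date and site of local treatment must be used. The analysis of local treatment already recommended by the steering committee should need much of the same information. Nothing here alters when local treatment may be given.

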Patients must have evidence of recovery from all prior cycle toxicity and the ANC must be > 1000/mm³ and platelets > 100 000/mm³ before receiving the next cycle of therapy. If initiation of the next treatment cycle is delayed by more than 2 weeks, the patients should be discontinued from the study.

In the absence of clinically progressive disease, patients should receive at least 2 cycles of VIT or VI prior to the first evaluation on study treatment.

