10.2. Trial Period

10.2.1 Treatment procedures for first two cycles

The following procedures must be performed prior to dosing with Temozolomide in combination with Vincristine and Irinotecan on the days indicated during weeks 1-6. Blood sampling will be made after application of topical anaesthetic cream, where appropriate.

Type of assessment	Delay for first 2 cycles (during weeks 1-6)

CLINICAL EXAM
 
 • Full physical examination • height, weight , body surface • Vital signs : blood pressure after 5 min at rest, heart rate, temperature • Performance status (Lansky Play Score or Karnofsky Score – appendix 3-4) • Assessment of adverse events according to the NCI-CTC AE v.4.0 (appendix 5) • Recording of concomitant medications 	
day 1

LABORATORY TESTS*
 
 • Complete blood count : white count (WBC), hemoglobin (HGB), hematocrit (HCT), differential count and platelet count • Serum chemistries : glucose, urea, creatinine, total protein, albumin, Ca+, phosphorus and electrolytes (sodium, potassium, chloride and bicarbonate), AST, ALT, total bilirubin, alkaline phosphatase, LDH, GGT 	
days 1, 8, 15
 
If aplasia, blood counts should be performed as clinically indicated

RADIOLOGICAL AND OTHER INVESTIGATIONS
 
 • Tumor assessments (CT scan and/or MRI) including measurement of target lesion and assessment of response to treatment should be loaded the CDs onto the PACS system for later review. • Bone scan or FDG-PET Scan** • BM aspirates and trephine biopsies** 	
Mandatory after cycle 2

STUDY TREATMENT
 
 • Administration of vincristine to patient, given intravenously prior the administration of Irinotecan on day 1 and day 8. • Administration of irinotecan to patient given by 60-intravenous infusion on days 1 through 5. • According to randomization, temozolomide will be given orally, on empty stomach, one hour prior to administration of irinotecan on days 1 through 5 	

**Not necessary on day 1 of cycle 1 if screening blood draw performed within 7 days of the first treatment.*

***only repeated if clinically indicated or if initially involved or to confirm tumor response*

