10.2.2 Treatment procedures for subsequent cycles

The following procedures must be performed prior to dosing with Temozolomide in combination with Vincristine and Irinotecan on the days indicated during weeks through all subsequent weeks that patient remains on study treatment (days 1, 8 and 15 based on 21 day cycles). Blood sampling will be made after application of topical anaesthetic cream, where appropriate.

Type of Assessment	Delay for subsequent cycles

CLINICAL EXAM
 
 • Full physical examination • height, weight , body surface • Vital signs : blood pressure after 5 min at rest, heart rate, temperature • Performance status (Lansky Play Score or Karnofsky Score – appendix 3-4) • Assessment of adverse events according to the NCI-CTC AE v.4.0 (appendix 5) • Recording of concomitant medications 	
day 1

LABORATORY TESTS
 
 • Complete blood count : white count (WBC), hemoglobin (HGB), hematocrit (HCT), differential count and platelet count 	
days 1, 8, 15.
 
If aplasia, blood counts should be performed as clinically indicated

 • Blood chemistry : glucose, creatinine, electrolytes (sodium, potassium, chloride and bicarbonate), AST, ALT, total and direct bilirubin, ASAT-ALAT, creatinine 	
day 1 if normal during cycles 1 and 2.
 
If significantly abnormal during cycle 1 or 2, blood chemistry should be taken on days 1, 8 and 15 for all subsequent cycles after cycle 2

RADIOLOGICAL AND OTHER INVESTIGATIONS
 
 • Tumor assessments (CT scan and/or MRI) including measurement of target lesion and assessment of response to treatment should be loaded the CDs onto the PACS system for later review. • Bone scan or FDG-PET Scan* • BM aspirates and trephine biopsies* 	
Mandatory after completion of every two cycles (must assess at 5 weeks after cycle 2 for responding or stable disease)

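### Read literally, time to treatment failure counts a progression-free patient who completes 12 on-schedule cycles (36 weeks) as a failure, because the definition's limit is one year

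*Protocol*

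**What the plan says.** Protocol section 11.1.3 (Secondary endpoints) runs TTF from the first administration of treatment to the earliest of several events. Besides documented progression, these are "discontinuation of study treatment before one year, or death, whichever occurs first". Nothing there separates stopping early from finishing the planned course.

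The protocol describes treatment duration in two ways:

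- Section 10.2.3 sets a cap: "The duration of study participation is a maximum of 12 cycles". It then loosens it: "the continuation of treatment can be individually discussed with the investigator for patients who do not experience progression of disease after 12 cycles".
- Section 9.1 gives no cap: "Treatment will continue until disease progression, unacceptable toxicity or the patient's desire to discontinue therapy". Appendix 1 also describes repeated cycles without a cap.

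Cycle length is three weeks in section 9.1, and section 10.2.2 schedules assessments on "days 1, 8 and 15 based on 21 day cycles". Delay is limited in section 9.1: "If initiation of the next treatment cycle is delayed by more than 2 weeks, the patients should be discontinued from the study".

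TTF is a named secondary objective (section 6.2). Since amendment 5.0, section 12.2 compares the two arms on all efficacy and safety endpoints, so TTF is now part of a between-arm comparison. The trial is open-label (section 7.1).

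**The concern.** A failure endpoint should count a stop for lack of benefit, toxicity or refusal. It should not count a patient who has received everything the protocol planned and has not progressed. Here the time limit for counting a stop as failure (one year) is longer than the capped course (36 weeks on schedule). The wording therefore takes in the most successful patients along with the failures.

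Two consequences follow if the text is applied as written. First, TTF says little after about week 36, because the remaining progression-free patients leave the curve as events when they complete treatment. Second, whether such a patient is an event depends on an individual decision to continue past cycle 12, taken by people who know the arm. A difference between arms in that practice would appear as a difference in TTF.

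**Working it through.** **Inputs (all Protocol).** Maximum 12 cycles (section 10.2.3). Cycle of 21 days (sections 9.1 and 10.2.2). Vincristine on day 8 is the last scheduled dose of a cycle (section 9.1). Delay of at most 2 weeks before a cycle (section 9.1). TTF limit of one year from first administration (section 11.1.3), taken as 365 days.

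**Check on the protocol's own figure.** Section 10.2.1 places the first two cycles in weeks 1 to 6. 2 × 21 = 42 days = 6 weeks, so the cycle-to-calendar conversion agrees with the protocol.

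**Length of the capped course.** 12 × 21 = 252 days = 36 weeks = 252/365.25 = 0.69 year, or about 8.3 months.

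**Shortfall against the limit.** 365 − 252 = 113 days, or 113/7 = 16.1 weeks. If the stop is dated by the last scheduled dose instead, that dose falls on study day 11 × 21 + 8 = 239, which is earlier still. Reaching one year on schedule would take 365.25/21 = 17.4, so 18 cycles.

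**Can permitted delays close the gap?** There are 11 intervals between 12 cycles.

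| | To end of cycle 12 | To last scheduled dose |
|---|---|---|
| On schedule | day 252 | day 239 |
| Mean delay per interval to reach day 365 | 113/11 = 10.3 days | (365 − 239)/11 = 11.5 days |
| Every interval delayed 14 days (11 × 14 = 154) | day 406 (58 weeks) | day 393 |

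Delay alone can therefore carry a patient past one year within the rules, but only if it averages about three quarters of the allowed maximum (10.3/14) over the whole course.

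**What the literal rule does to the curve.** Let *c* be the proportion of an arm still event-free and on treatment at the end of cycle 12, and *e* the fraction of those who are extended. Leaving aside patients with the long delays above, literal TTF at one year is at most *c* × *e*. With *e* = 0 it is zero; with *e* = 1 it can be as high as *c*. The protocol gives neither *c* nor *e*, so the late part of the curve cannot be predicted and depends on extension practice as well as on the drugs.

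**The case against.** The strongest reply is that discontinuation means stopping for cause. The protocol tends to use the word that way: the dose-modification tables discontinue for toxicity, section 9.1 for excessive delay, and section 13.9 gives progression and a switch to other treatment as example reasons. The withdrawal list in section 7.8 does not include completing treatment, and the heading of section 10.2.3 names end of treatment and withdrawal separately. This reading is plausible, and it makes the fault an ambiguity for anyone who adopts it. It does not dispose of the point. No passage states it, and a one-year window does not fit as the marker of prematurity for a 36-week course.

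A second reply is that section 9.1 and Appendix 1 set no cap and section 10.2.3 allows extension, so not every progression-free patient stops at cycle 12. That is correct. It limits the size of the effect and shows that the protocol disagrees with itself on duration. It does not make the TTF definition sound.

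Three stronger inferences are not supported:

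- **TTF at 12 months is zero in both arms whatever the drugs do.** This requires that nobody is extended and nobody accumulates long delays. The protocol permits both.
- **The better arm is penalised.** A completer's event falls at about week 36, later than the event of a patient who progressed or stopped before then. More completers still means a higher curve up to that time. What is lost is information after it; the arms are not reversed.
- **Every responder who goes on to local treatment is a failure.** Section 9.1 allows local treatment after two cycles, section 7.8 does not list it as a reason for withdrawal, and the version 5.1 amendment note records that this criterion was removed. Only patients who actually stop study treatment for it are affected, and their number is unknown.

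**Conclusion.** The point holds in a limited form. As worded, section 11.1.3 scores a progression-free patient who completes 12 cycles and is not extended as a failure at about 8.3 months, 113 days before the one-year limit. The exception is a patient whose delays average about 10.3 days or more per interval. This rests on three assumptions: discontinuation is read literally, the 12-cycle maximum in section 10.2.3 is applied, and the course end is dated at the end of cycle 12.

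The damage is loss of TTF information after about week 36, with late events depending on open-label decisions to extend. Its size cannot be given, because the protocol does not say how many patients reach cycle 12 or are extended.

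Severity is minor to moderate. TTF is a secondary endpoint. The response-based decision rule and sample size do not use it, and neither PFS nor OS has a discontinuation component, so durable benefit is still measured elsewhere.

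**What to change.** In section 11.1.3, define the TTF event as progression, death, or discontinuation of study treatment for any reason other than completing the protocol-planned course without progression. State that such completers are not events at completion and remain in follow-up for progression or death. This wording replaces the one-year limit and takes no position on how long the planned course should be.

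Tabulate by arm the stops associated with local treatment, so that a reader can see how much of TTF they account for.

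Reconcile sections 9.1, 10.2.3 and 11.1.3 and Appendix 1 on planned treatment duration. Which duration applies is for the sponsor and investigators to settle; this review does not choose.

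The cost is about one sentence of definition plus the reconciliation. Section 13.9 already asks sites to record cycle dates and, where applicable, the date and reason for discontinuation, so no new data item should be needed beyond making sure that completion can be told apart from other reasons. The change should be made before TTF is analysed by arm, because a later redefinition could look data-driven.
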